8.1. Efficacy analysis

COVID-19 incidence in subjects will be assessed using two separate metrics. The number and percentage of subjects who had (1) a positive nasal swab SARS-CoV-2 PCR test during the study and (2) an Adverse Event with a MedDRA preferred term of "COVID-19", "Asymptomatic COVID-19", or "COVID-19 pneumonia" will be summarized for the SAF.

For both measures, the incidence rate (IR) is defined as the number of subjects with an event divided by the number of subjects at risk and person-days adjusted by person-years (total time at risk). The IR's of subjects with (1) positive PCR and (2) MedDRA preferred terms indicating COVID-19 will be reported in the fashion of 100 person-years (see the [formula below](#)).

$$IR = \frac{\text{number of subjects with positive PCR}}{\text{sum(Person - days at risk)}} * 365.25 * 100$$

Person-Days at risk are defined as the total time from injection date of prime dose to the date of the positive PCR test for (1) or AE start date for (2), last date of study participation, data cutoff date, whichever is the earliest. The respective 95% CIs of positive nasal swab SARS-CoV-2 PCR tests and COVID-19-related adverse events will be calculated using the Clopper-Pearson [6] method.

8.2. Immunogenicity Analysis

Not applicable for this statistical analysis plan and will be described in a separate SAP.

9. Safety Analysis

All safety summaries and analyses will be conducted for the Safety Analysis Set.

Safety data will be presented by actual treatment received at Prime dose (prior to Booster) and by actual Booster dose received (on or after Booster).

Safety will be assessed by the frequency and severity of:

- SAEs occurring after signing of the informed consent form (ICF) throughout the entire study.
- Solicited AEs (reactogenicity events occurring from the time GRT-R910 vaccination through 7 days after GRT-R910 vaccination).
- Reactogenicity local reactions (including erythema, induration/edema, pain, and tenderness).
- Reactogenicity systemic reactions including fever, chills, fatigue, malaise, myalgia, arthralgia, headache, and nausea.
- Clinical safety laboratory AEs occurring from the time of GRT-R910 vaccination through approximately 7 days after GRT-R910 vaccination. Parameters to be evaluated include WBC, Hb, PLT, ALT, AST, ALP, total bilirubin, CK, and creatinine.
- Unsolicited AEs (non-serious AEs occurring from the time of GRT-R910 vaccination through approximately 28 days after GRT-R910 vaccination).
- AESIs (including serologically or virologically confirmed SARS-CoV-2 infection and severity of COVID-19 and the comorbidity with PIMMCs, MAAEs, and NOCMCs occurring from the time of the first study vaccination throughout the entire study) [2].

Assessments of cardiac biomarkers (see 9.4), body system evaluations through physical exams (see 9.5), and electrocardiograms (ECG; section 9.6) will also be used to assess safety. Interpretations that are missing or otherwise not done will be reported as counts, but will not be included in the denominator.

9.1. Adverse Events

Adverse Event (AE) means any untoward medical occurrence associated with the use of an intervention in humans, whether or not considered intervention-related in a patient or clinical investigation subject administered a pharmaceutical product regardless of its causal relationship to the study treatment.

An AE can therefore be any unfavorable and unintended sign (including an abnormal laboratory finding), symptom or disease temporarily associated with the use of a medicinal (investigational) product. The occurrence of an AE may come to the attention of study personnel during study visits and interviews of a study recipient presenting for medical care, or upon review by a study monitor. AEs, including solicited local and systemic (subjective and quantitative) reactions, not meeting the protocol-defined criteria for SAEs will be recorded on the appropriate DCF and entered into the

eCRF. Information to be collected for unsolicited non-serious AEs includes event description, date of onset, licensed study physician's assessment of severity and relationship to GRT-R910 or alternate etiology (if not related to study product) (assessed only by those with the training and authority to make a diagnosis (date of resolution, seriousness, and outcome. AEs occurring during the trial collection and reporting period will be documented appropriately regardless of relationship to GRT-R910. AEs will be followed through resolution.

Any medical condition that is present at the time that the subject is screened will be considered as baseline and not reported as an AE. However, if the severity of any pre-existing medical condition increases, it should be recorded as an AE.

A treatment-emergent AE (TEAE) is defined as any new AE that begins after the first vaccination or any pre-existing condition that worsens in severity. A treatment related adverse event (TRAЕ) is defined as any AE that is deemed to be related to the vaccination.

Adverse events consist of solicited AEs (local and systemic), unsolicited treatment-emergent AEs, treatment-related AEs, severe AEs, SAEs, MAAEs, AESIs, AEs leading to withdrawal from study participation.

All AEs will be coded using the MedDRA (version to be delineated in the CSR), including System Organ Class (SOC) and Preferred Term (PT) names. Summary by SOC and PT will be shown in some tables. The data will also include AEs based on laboratory assessment (if applicable). All AEs will be followed through resolution.

Only TEAEs will be included in summary tables and will be summarized by cohort and vaccination (Vaccination Dose 1, Vaccination Dose 2, entire study period). Percentages will be based upon the number of participants in the Safety Analysis Set within each cohort. A subject may have more than 1 AE for an SOC or PT. A subject with 2 or more AEs within the same level of summarization will be counted only once in that level 1

The rules described in [Table 4](#) will be applied for AEs partial dates during this study to understand if it is TEAE. No other data will be imputed.

All AEs will be reported by data listings for the SAF.

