- From a patient compliance standpoint in Cohorts 1 and 2, a single dose of GRT-R910 following the initial 2 injections of AstraZeneca's first-generation COVID-19 vaccine is deemed an acceptable option for subjects ≥ 60 years of age if they are not willing to receive a second dose of GRT-R910.

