3 ^c	10	10 mcg ^d	10 mcg
4 ^c	10	10 mcg ^d	10 mcg
6 ^e	10 ^e	10 mcg ^d	10 mcg
TOTAL	50		

a Healthy adults aged ≥ 60 years at least 2 months after receiving AstraZeneca's COVID-19 prime and boost vaccine.

b Cohort will include 2 sentinel subjects.

c Healthy adults aged ≥ 60 years at least 2 months after receiving an adenoviral COVID-19 vaccine (Cohort 3) or an mRNA based COVID-19 vaccine (Cohort 4).

d Dose selected from Cohorts 1 and 2.

e Healthy adults ≥ 18 to ≤ 59 years of age at least 2 months after receiving an mRNA based COVID-19 vaccine (Cohort 6).

4. General Statistical Considerations

All data collected will be presented in data listings sorted by cohort and subject, and when appropriate by study days number within subject. Data from subjects excluded from an analysis

set will be presented in the data listings but not included in the calculation of summary statistics for that analysis set.

Summary statistics for continuous variables will include the number of patients/observations (n), mean, standard deviation, median, minimum, and maximum. Categorical data will be summarized by cohort using frequency and percentages. Unless otherwise stated, the denominator of percentages will be the number of participants in the population of interest and cohort. The number of missing values will be presented as a separate category but will only be displayed if one or more subjects are missing data. Counts of zero will be presented without percentages.

Any additional exploratory analysis not defined in the SAP will be identified in the final CSR as exploratory post hoc analysis, including analyses for additional study populations or subgroups of interest.

All data processing, summarization, and analyses will be performed using SAS Environment/ Version 9.4 or later of the SAS® statistical software package [3]

Unless otherwise stated, the principles below will be applied:

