Descriptive Summary Statistics for Continuous Variables	
Descriptive statistics will include the number of non-missing values (n), arithmetic mean, standard deviation (SD), median, minimum (min), and maximum (max) values.
 
The minimum and maximum values will be displayed to the same decimal precision as the source data the arithmetic mean, median, values will be displayed to one more decimal than the source data, and the SD values will be displayed to two more decimals than the source data for the specific variable.
 
The maximum number of decimal places in the statistical report is four. If some descriptive statistical value has more than four decimal places after the application of the above-mentioned rules, this value will be rounded to four decimal places.
 
The appropriate precision for derived variables will be determined based on the maximum precision of the data on which the derivations are based, and statistics will be presented following the above-mentioned rules.

Descriptive Summary Statistics for Categorical Variables	
Descriptive statistics will include frequencies and percentages per category as well as clinical evaluations (normal, abnormal, and not clinically significant, abnormal, and clinically significant). The denominator in all percentage calculations will be the number of subjects in the relevant analysis population in the corresponding treatment group with non-missing data unless specifically stated otherwise.
 
Percentages will be rounded to one decimal place

Significance Test	
The default significance level will be 0.05 (5%); all tests are two-sided (where applicable) unless otherwise specified in the description of the analysis.

Confidence Intervals (CIs)	
The default CIs will be 95% and will be determined using the Clopper-Pearson method [6].

Principle/definition	Value
p-values	All p-values will be presented to 3 decimal places and values less than 0.001 or greater than 0.999 will be presented as <0.001 and >0.999, respectively.

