4.5.3. Safety Analysis Set (SAF)

The Safety Analysis Set (SAF) will contain all subjects in AES who received at least 1 dose of GRT-R910.

Summaries and analysis of safety data will be presented for the Safety Analysis Set. Subjects will be analyzed according to their actual treatment.

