7.2. Study Vaccine Administration

Depending on the Cohort, study vaccination will be comprised of one or two intramuscular (IM) injections in the deltoid muscle of the subject's preferred arm. For Cohorts 1 and 2, initially subjects began the study only planning to receive one dose. In order to receive a booster dose, each subject needed to sign another ICF.

The number of doses received will be summarized for the SAF using descriptive statistics for qualitative variables. In addition, the vaccine administration data will be presented in a data listing.

8. Efficacy and Immunogenicity Analysis

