The number and percentage (with 95% Clopper-Pearson CIs [6]) of participants who reported any solicited AE on the vaccination day and through the 7 subsequent days (see the exact windows for each cohort in [Table 5](#)) will be tabulated by grade and treatment group for each vaccination. Percentages will be based upon the number of participants in the Safety Analysis Set within each vaccination group. Subjects will be counted once for the most severe event in cases where the subject reported more than one event per solicited AE category (e.g., injection site pain). In addition, the duration (in days) of solicited AEs after each vaccination will be summarized by treatment group for each vaccination. Duration will be calculated as the number of days of the Solicited AE during the special window ([Table 5](#)).

Table 5 Windows for solicited AEs per Cohort

Cohort	Vaccination Day	Windows for Solicited AEs
1 and 2 (Subjects NOT RECEIVING booster dose)	Day 1	Day 1 through Day 8
1 and 2 (Subjects RECEIVING booster dose)	Day 1	Day 1 through Day 8
	Day 113	Day 113 through Day 120
3, 4, and 6	Day 1	Day 1 through Day 8
	Day 29	Day 29 through Day 36

All solicited local and systemic AEs will be presented in the data listings, including a listing of solicited AEs.

Calculation of Solicited AEs duration

The number of days will be calculated at the level of subject, vaccination (prime or booster), and symptom as the longest duration of consecutive days after the injection (including the day of injection) the subjects' reported solicited AE occurs with a toxicity grade > 0. If the solicited AE continues beyond 8 days, the days from the solicited AE reported after 8 days will be included (e.g., an event that lasted 5 days in the first 8 days post injection and 4 days beyond 8 days post injection, the duration will be reported as >8 days). A separate example below illustrates how solicited AE duration is calculated:

Subject ID	Prime/Booster	Symptom	Timepoint	Severity	Grade
G0910000999	DOSE 1	Headache	Day 1	MILD	1
G0910000999	DOSE 1	Headache	Day 2	MILD	1
G0910000999	DOSE 1	Headache	Day 3	NONE	0
G0910000999	DOSE 1	Headache	Day 4	NONE	0
G0910000999	DOSE 1	Headache	Day 5	MILD	1

G0910000999	DOSE 1	Headache	Day 6	MODERATE	2
G0910000999	DOSE 1	Headache	Day 7	MODERATE	2
G0910000999	DOSE 1	Headache	Day 8	MILD	1
G0910000999	DOSE 1	Headache	Day 9	MILD	1
G0910000999	DOSE 1	Headache	Day 10	NONE	0

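### SAP 9.1 divides Dose 2 adverse-event percentages by the whole cohort, so booster-period unsolicited rates are too low if any Cohort 1 or 2 subject declined the optional booster

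*SAP*

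**What the plan says.** SAP 9.1 summarizes treatment-emergent events by cohort and by vaccination, with separate summaries for Dose 1, Dose 2 and the entire study period. The next sentence gives the only denominator: "Percentages will be based upon the number of participants in the Safety Analysis Set within each cohort". SAP 4.5.3 defines that set as one that "will contain all subjects in AES who received at least 1 dose of GRT-R910".

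The second dose was optional in Cohorts 1 and 2. Protocol 4.3.1 treats a single dose as acceptable for these subjects "if they are not willing to receive a second dose of GRT-R910". SAP 7.2 says they entered the study planning one dose, and adds: "In order to receive a booster dose, each subject needed to sign another ICF". Both documents carry a separate visit schedule for Cohort 1 and 2 subjects who are not boosted, and SAP 5.1 counts those who consented to the booster period.

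Other places in the SAP bear on the denominator:

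- SAP 9 (opening text) presents safety data from the booster onward "by actual Booster dose received (on or after Booster"), without naming a denominator.
- SAP 9.1.2, for solicited events: "Percentages will be based upon the number of participants in the Safety Analysis Set within each vaccination group".
- SAP 4, the general default: "the denominator of percentages will be the number of participants in the population of interest and cohort".
- SAP 4.2, Table 2: the relevant population "in the corresponding treatment group with non-missing data unless specifically stated otherwise".

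**The concern.** A percentage for the period after Dose 2 should be taken over people who received Dose 2. Under SAP 9.1 as written, prime-only subjects add to the denominator and can never add to the numerator. Every non-zero Dose 2 unsolicited percentage is then too low for any cohort with a decliner.

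Three consequences follow:

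- The prime and booster tables are produced as pairs and will be read side by side. Diluting only the booster column can make the second dose look better tolerated than the first when it is not.
- Solicited and unsolicited booster results for the same cohort would rest on different denominators, if vaccination group in SAP 9.1.2 carries its natural meaning of those who received that vaccination. SAP 9.1 also counts solicited events among adverse events, so the two rules overlap.
- Protocol 12.4.2 calls for exact 95% confidence intervals on adverse-event proportions. Any such interval computed per dose would use too large an n. For events not seen at all, it would overstate how much risk has been excluded.

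**Working it through.** **Inputs.** Planned cohort size is 10 (SAP 4.3). The default interval is 95% Clopper-Pearson (SAP 4.2, Table 2). The number boosted per cohort, m, is not in the documents and is varied here as an assumption.

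**The plan's own figure.** SAP 4.3 gives an 89% chance of at least one event in a group of 10 at a true rate of 20%. This reproduces: 1 − 0.8^10 = 89.26%. It holds only for 10 exposed subjects. After the booster it becomes 1 − 0.8^m: 83.22% at m = 8 and 67.23% at m = 5.

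**Size of the bias.** With x subjects having an event after Dose 2, SAP 9.1 reports x/10 and the rate among those boosted is x/m. Since x/10 = (x/m) × (m/10), the reported figure is the boosted rate times m/10, a relative understatement of (10 − m)/10.

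| m boosted | Factor m/10 | Two events, SAP 9.1 (95% CI) | Two events, boosted only (95% CI) | Zero events, upper limit on n = m |
|---|---|---|---|---|
| 10 | 1.0 | 20.0% (2.5 to 55.6) | 20.0% (2.5 to 55.6) | 30.8% |
| 9 | 0.9 | 20.0% (2.5 to 55.6) | 22.2% (2.8 to 60.0) | 33.6% |
| 8 | 0.8 | 20.0% (2.5 to 55.6) | 25.0% (3.2 to 65.1) | 36.9% |
| 7 | 0.7 | 20.0% (2.5 to 55.6) | 28.6% (3.7 to 71.0) | 41.0% |
| 5 | 0.5 | 20.0% (2.5 to 55.6) | 40.0% (5.3 to 85.3) | 52.2% |

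The zero-event limit is 1 − 0.025^(1/n). Under SAP 9.1 it would be 30.8% whatever the uptake.

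**Total column.** Assuming all 30 subjects in Cohorts 3, 4 and 6 were boosted, the factor is (m1 + m2 + 30)/50. That is 48/50 = 0.96 with 9 + 9 boosted in Cohorts 1 and 2, 46/50 = 0.92 with 8 + 8, and 40/50 = 0.80 with 5 + 5.

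**10 versus 30 mcg.** Suppose the true rate among boosted subjects is 40% at both doses. With 8 of 10 boosted in each cohort, both show 0.40 × 0.8 = 32%. With 5 of 10 boosted at 10 mcg and 10 of 10 at 30 mcg, the tables show 20% and 40%. Reversing the uptake reverses the gap, so the distortion has no fixed direction.

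**Do the general rules settle it?** No. The SAP 4 default points to the cohort, as SAP 9.1 does. The treatment-group rule in SAP 4.2, Table 2 gives way where another rule is stated, and SAP 9.1 states one. In Appendix 2 the laboratory, vital-sign, cardiac biomarker and ECG tables separate Cohorts 1 and 2 by booster status where booster status matters. The booster-period unsolicited tables name only the Safety Analysis Set.

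**The case against.** The best defence is that the opening of SAP 9 governs all safety output. If booster-period data are shown by the booster dose actually received, and SAP 4.5.3 analyzes subjects by actual treatment, a prime-only subject belongs in no booster column, and the cohort denominator could mean the cohort's subjects within that column. That reading is possible. But SAP 9 names no denominator, and SAP 9.1 is the specific sentence that does. If boosted-only was meant, the sentence still needs the same edit.

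Several other points stand and limit the weight of the issue:

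- Vaccination group in SAP 9.1.2 is undefined, so the conflict with 9.1 rests on its natural reading.
- The SAP's unsolicited-event sections plan counts and percentages without stating intervals, and Protocol 12.4.2 does not ask for them per dose. The interval figures above apply only if such intervals are produced.
- No hypothesis tests between cohorts are planned, the 10 mcg dose was chosen on single-dose data, and the halting rules count subjects. No stated decision turns on a Dose 2 unsolicited percentage.
- Counts accompany the percentages and the number of doses received is tabulated, so a careful reader could recompute the rates.

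These points keep the matter from being critical. They do not make the stated denominator right.

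**Conclusion.** The concern holds. As written, SAP 9.1 understates every non-zero Dose 2 unsolicited percentage by the share of the cohort not boosted: 10% in relative terms with one decliner in 10, 20% with two, 50% with five, and nothing if all were boosted. Actual uptake is not in the documents, so the size is a range. The calculations assume 10 treated per cohort.

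The primary endpoint as worded, unsolicited events within 28 days of the last dose a subject received, is not affected, because every Safety Analysis Set subject is at risk for it. The separate Dose 2 breakdown is. This should be corrected before the tables are run: characterizing safety is the study's purpose, and with 10 per cohort a single decliner moves every non-zero booster percentage.

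**What to change.** Replace the denominator sentence in SAP 9.1 with:

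> Percentages for Dose 1 and the entire study period use the Safety Analysis Set within each cohort; percentages and any exact CIs for Dose 2 use Safety Analysis Set subjects in the cohort who received Dose 2.

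Apply it to Tables 14.3.1.7.2, 14.3.1.8.2, 14.3.1.9.2, 14.3.1.14.2 and 14.3.1.15.2, and show the number boosted as the column N. The wording also covers any Cohort 3, 4 or 6 subject who missed the second dose. Defining vaccination group in SAP 9.1.2 in the same terms would complete the alignment with solicited events.

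The cost is one SAP sentence and a denominator flag in the table programs, with no new data. Dose 2 percentages are multiplied by 10/m: 1.11 at m = 9, 1.25 at m = 8, 2 at m = 5, and unchanged at m = 10.

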9.1.1. Unsolicited Adverse Events

Unsolicited non-serious AEs will be captured for 28 days following each GRT-R910 vaccination. Unsolicited adverse events may be recorded beyond 28 days, but only AEs occurring within 28 days of treatment vaccination will be summarized. In addition, SAEs and AESIs, including PIMMCs, MAAEs, and NOCMCs, will be captured throughout the entire study following GRT-R910 vaccination. Incidence of Unsolicited Adverse Events

An overall summary of unsolicited TEAEs through 28 days after GRT-R910 vaccination (1st dose and/or booster dose) including the number and percentage of subjects who experienced the following will be presented:

- Any unsolicited TEAEs
- Any unsolicited Treatment-Related TEAEs

- Any serious TEAEs
- Any serious Treatment-Related TEAEs
- Any unsolicited severe TEAEs
- Any Treatment-Related severe TEAEs
- Any unsolicited AESIs

An overall summary of the following AEs will be presented throughout the entire study:

- Any serious AEs
- Any unsolicited medically attended TEAEs (MAAEs)
- Any unsolicited AESIs: severe COVID-19
- Any unsolicited AESIs: PIMMCs
- Any unsolicited AESIs: NOCMs
- Any unsolicited AESIs: Serologically or Virologically Events Confirmed Relevant to COVID-19
- Any Treatment-Related AEs
- Any Treatment-Related MAAEs
- Any Treatment-Related unsolicited AESIs: severe COVID-19
- Any Treatment-Related AESIs: PIMMCs
- Any Treatment-Related AESIs: NOCMs
- Any Treatment-Related unsolicited AESIs: Serologically or Virologically Events Confirmed Relevant to COVID-19

All the categories above will be summarized by SOC and PT separately.

In addition, separate listings containing individual subject adverse event data for unsolicited AEs, unsolicited TEAEs leading to discontinuation from participation in the study or study treatment, serious AEs and unsolicited MAAEs will be provided separately.

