11.1.1.2 Unsolicited Adverse Events

Unsolicited non-serious AEs will be captured for 28 days following each GRT-R910 vaccination. In addition, AESIs, including PIMMCs, MAAEs, and NOCMCs, will be captured throughout the entire study following GRT-R910 vaccination.

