11.2 Reporting Procedures

Solicited local and systemic reactogenicity events will be documented and reported from the time of GRT-R910 vaccination through 7 days after GRT-R910 vaccination.

Clinical safety laboratory AEs will be documented and reported before GRT-R910 vaccination and 7 days after each GRT-R910 vaccination.

Unsolicited non-serious AEs will be documented and reported from the time of the GRT-R910 vaccination through 28 days after each GRT-R910 vaccination.

AESIs including PIMMCs/MAAEs/NOCMCs will be documented and reported from the time of the initial GRT-R910 vaccination throughout the entire study.

SAEs occurring after signing of the ICF will be recorded and reported to the sponsor or designee by the investigator within 24 hours of becoming aware of the SAE. If the SAE occurs after signing of the ICF and before the first (prime) dose, it will be reported on the medical history eCRF. If the SAE occurs after the first (prime) dose, it will be reported on the AE eCRF.

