15	Table	14.3.1.4.3	Summary of Duration (Days) of Solicited Adverse Events Related to the Injection of Prime Dose	Safety Analysis Set
16	Table	14.3.1.4.4	Summary of Duration (Days) of Solicited Adverse Events Related to the Injection of Booster Dose	Safety Analysis Set
17	Table	14.3.1.5.1	Summary of Subjects with Solicited Adverse Events Beyond 8 Days Related to the Injection of Prime Dose by Maximum Grade	Safety Analysis Set
18	Table	14.3.1.5.2	Summary of Subjects with Solicited Adverse Events Beyond 8 Days Related to the Injection of Booster Dose by Maximum Grade	Safety Analysis Set
19	Table	14.3.1.6.1	Summary of Unsolicited TEAEs Throughout the Study	Safety Analysis Set
20	Table	14.3.1.7.1	Subject Incidence of Unsolicited TEAEs by Maximum Severity, System Organ Class and Preferred Term up to 28 Days After the Injection of Prime Dose	Safety Analysis Set
21	Table	14.3.1.7.2	Subject Incidence of Unsolicited TEAEs by Maximum Severity, System Organ Class and Preferred Term up to 28 Days After the Injection of Booster Dose	Safety Analysis Set
22	Table	14.3.1.8.1	Subject Incidence of Unsolicited TEAEs by System Organ Class and Preferred Term up to 28 Days After the Injection of Prime Dose	Safety Analysis Set

Gritstone bio, Inc.
GO-009Statistical Analysis Plan, Version 5.0
Date Issued: 09JUN2023

23	Table	14.3.1.8.2	Subject Incidence of Unsolicited TEAEs by System Organ Class and Preferred Term up to 28 Days After the Injection of Booster Dose	Safety Analysis Set
24	Table	14.3.1.9.1	Subject Incidence of Unsolicited Treatment-Related TEAEs by System Organ Class and Preferred Term up to 28 Days After the Injection of Prime Dose	Safety Analysis Set
25	Table	14.3.1.9.2	Subject Incidence of Unsolicited Treatment-Related TEAEs by System Organ Class and Preferred Term up to 28 Days After the Injection of Booster Dose	Safety Analysis Set
26	Table	14.3.1.10	Subject Incidence of Unsolicited TEAEs by System Organ Class and Preferred Term Throughout the Study	Safety Analysis Set
27	Table	14.3.1.11	Subject Incidence of Unsolicited Treatment-Related TEAEs by System Organ Class and Preferred Term Throughout the Study	Safety Analysis Set
28	Table	14.3.1.12	Subject Incidence of Serious TEAEs by System Organ Class and Preferred Term Throughout the Study	Safety Analysis Set
29	Table	14.3.1.13	Subject Incidence of Serious Treatment-Related TEAEs by System Organ Class and Preferred Term Throughout the Study	Safety Analysis Set

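### SAP 9.1.1 limits summaries of unsolicited AEs to 28 days after a dose, but SAP 9.1, 9.1.1.1, 9.1.1.2 and Table 9 items 26 and 27 call for whole-study tables that would include incompletely collected events

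*SAP*

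**What the plan says.** **Collection.** Protocol 11.1.1.2: "Unsolicited non-serious AEs will be captured for 28 days following each GRT-R910 vaccination". Protocol 11.2 repeats the rule for reporting: "Unsolicited non-serious AEs will be documented and reported from the time of the GRT-R910 vaccination through 28 days after each GRT-R910 vaccination". For other event types SAP 9.1.1 states: "SAEs and AESIs, including PIMMCs, MAAEs, and NOCMCs, will be captured throughout the entire study following GRT-R910 vaccination".

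**Summaries limited to 28 days.** SAP 9.1.1 allows later unsolicited AEs to be recorded, but says that "only AEs occurring within 28 days of treatment vaccination will be summarized". The primary endpoint for unsolicited AEs (protocol section 5, SAP section 2) also has a 28-day window.

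**Summaries over the whole study.** SAP 9.1 says that TEAEs "will be summarized by cohort and vaccination (Vaccination Dose 1, Vaccination Dose 2, entire study period"). SAP 9.1.1.1 and 9.1.1.2 plan tables of all TEAEs by relationship and by severity, each with a separate 28-day summary. The whole-study list in SAP 9.1.1 has a row for treatment-related AEs of any kind. SAP Appendix 2, Table 9, item 26 is titled "Subject Incidence of Unsolicited TEAEs by System Organ Class and Preferred Term Throughout the Study"; item 27 is its treatment-related counterpart. Item 19 is titled "Summary of Unsolicited TEAEs Throughout the Study".

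**The concern.** A programmer cannot follow both rules. SAP 9.1 defines a TEAE as starting after the first vaccination and sets no upper time limit, so an all-TEAE table over the study would admit any late event in the database.

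Non-serious events that are not AESIs have no scheduled collection outside the 28-day windows. A whole-study percentage for them would therefore combine a period in which every subject is asked with a period in which recording depends on whether an event happens to surface. SAP 9.1 bases percentages on subjects in the Safety Analysis Set within each cohort, not on person-time. Follow-up is 7, 12, up to 13 or 16 months, and subjects in Cohorts 1 and 2 may have had one dose or two. A reader of the study report could take these columns as complete incidences and compare them across cohorts.

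**Working it through.** The plan gives no figure for this point, so the check compares passages and then computes calendar coverage.

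**1. Which outputs conflict (SAP 9.1.1 against Table 9)**
- The 28-day list in 9.1.1 has a row for any unsolicited TEAE. The whole-study list does not. Item 26 therefore has no counterpart in 9.1.1.
- Item 27 agrees with the treatment-related row of the whole-study list, but that row contradicts the 28-day restriction in the same section.
- Item 19 fits the whole-study list. Apart from the treatment-related row, its rows are event types collected to study end.
- SAP 9.1.1 promises an overall 28-day summary. Table 9 contains none.
- Items 20 to 25 and 30 to 33 (28 days after each dose) agree with the rule. Items 28, 29 and 34 to 43 (serious events, AESIs, MAAEs, PIMMCs, NOCMCs, COVID-19 events) rest on whole-study collection.

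**2. When non-serious AEs are scheduled for collection (SAP Tables 6 to 8)**
- Cohorts 1 and 2 without booster: to V05, Day 29.
- Cohorts 1 and 2 with booster: to V05, then from V07 (Day 113) to V11 (Day 142). There is no AE entry at V06 (Day 57). The gap is 113 − 29 = 84 days, or 134 − 29 = 105 days if the second dose is given at +21 days. Unscheduled visits before V11 can still yield AEs in this gap.
- Cohorts 3, 4 and 6: to V10, Day 58. The two windows adjoin.

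**3. Calendar coverage**

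Coverage = (28 × doses) / (last visit day − 1).

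| Group | Calculation | Coverage |
|---|---|---|
| Cohorts 1/2, no booster, Day 365 | 28/364 | 7.7% |
| Cohorts 1/2, booster, Day 478 | 56/477 | 11.7% |
| Cohorts 3/4, to Day 394 | 56/393 | 14.2% |
| Cohorts 3/4, if last visit is Day 209 | 56/208 | 26.9% |
| Cohort 6, Day 209 | 56/208 | 26.9% |

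**4. Illustration of non-comparability (assumed inputs, not from the documents)**

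Let λ be the rate of affected AEs per person-year, equal in all cohorts, and f the share of out-of-window events that are recorded. With w days covered out of T:

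P(at least one recorded) = 1 − exp(−λ[w + f(T − w)]/365.25).

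For example, Cohort 6 with λ = 1 and f = 0.5: 1 − exp(−[56 + 0.5 × 152]/365.25) = 30.3%.

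| λ = 1 | f = 0 | f = 0.5 | f = 1 |
|---|---|---|---|
| Cohorts 1/2, no booster | 7.4% | 41.5% | 63.1% |
| Cohorts 1/2, booster | 14.2% | 51.8% | 72.9% |
| Cohorts 3/4 to Day 394 | 14.2% | 45.9% | 65.9% |
| Cohort 6 | 14.2% | 30.3% | 43.4% |

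For λ from 0.5 to 2 at f = 0.5, boosted Cohorts 1/2 range from 30.6% to 76.8% and Cohort 6 from 16.5% to 51.5%. The same underlying rate gives different percentages. The f = 1 column shows that unequal follow-up alone does this even with complete recording.

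**The case against.** **Table 9 gives titles, not selection rules.** SAP 9.1.1 could itself be the selection rule: non-serious events within 28 days, plus SAEs and AESIs throughout. Under that reading, items 26 and 27 already hold the right events and lack only a footnote. This is possible, and it stands to the extent that the mixture is a consequence of following the text literally, not an established fact. It does not settle the matter, because 9.1, 9.1.1.1 and 9.1.1.2 point the other way.

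**Most events that matter are collected to the end.** An MAAE covers unscheduled contact with medical personnel whatever the cause, and MAAEs count as AESIs. What lacks scheduled collection is therefore non-serious, not medically attended, not chronic and not otherwise of special interest. This stands and narrows the point considerably.

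**Late events are not left wholly to chance.** Interim medical history is reviewed at every visit, and protocol 7.2.4 asks for new clinically relevant findings to be reported as AEs. This stands in part. It makes some late recording likely, which is why the late data would be incomplete and not simply absent.

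**Item 19 is largely sound.** This stands; only its treatment-related row is affected.

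**Little depends on it.** The primary unsolicited-AE endpoint is served by the per-dose 28-day tables, and no between-cohort testing is planned. This stands and limits the importance of the point, but the tables would still be published.

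**Conclusion.** The SAP contradicts itself on whether non-serious, non-AESI unsolicited events after 28 days are tabulated. If the whole-study wording is followed, items 26 and 27 and one row of item 19 would report percentages that are not complete whole-study incidences and that vary with unscheduled recording, number of doses and follow-up length. This is a moderate reporting defect, worth correcting before the outputs are produced.

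A reader might infer three stronger conclusions that the documents do not support:
- That coverage of about 8% to 27% means most late adverse events are missed. These figures are shares of calendar time, and SAEs and AESIs are collected throughout.
- That all whole-study safety tables are unreliable. Those for SAEs, MAAEs, PIMMCs, NOCMCs and other AESIs have matching collection, although their subject percentages still reflect unequal follow-up.
- That the primary endpoint is compromised. The 28-day tables after each dose are untouched.

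The conflict itself rests on the text alone. Only the illustrative percentages depend on the assumed λ and f and on a constant event rate.

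**What to change.** 1. Define items 26 and 27, and the treatment-related row of item 19, as non-serious unsolicited TEAEs within 28 days of either dose plus SAEs and AESIs (including MAAEs, PIMMCs and NOCMCs) at any time. For item 27 and that row, take the treatment-related subset.
2. Retitle items 26 and 27 to say so.
3. Footnote the collection windows, the number of doses received and the follow-up length by cohort. The new definition does not remove differences in exposure, so the footnote is needed as well.
4. Align SAP 9.1, 9.1.1, 9.1.1.1 and 9.1.1.2 with this definition.
5. Add to Table 9 the overall 28-day summary that SAP 9.1.1 promises.
6. Show later non-serious, non-AESI events in listings only.

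The cost is one selection flag, the new titles and footnotes, one added summary table and short text edits. No new data are collected, and no sample size figure changes.
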